For cannabis user groups, we must recruit participants that have previously or currently used marijuana products and have a desire to continue or begin using any of the ratios and potencies potentially assigned during the study period. Thus, assignment to the all THC strain (+THC/-CBD, 1:0) serves as a naturalistic control group and our primary hypotheses surround effects of switching anxious marijuana users to either a strain with THC and CBD (e.g., +THC/+CBD, 1:1) or to a CBD-based strain without THC (i.e., -THC/+CBD, 0:1,), which are both likely to reduce anxiety symptoms over 4 weeks of use. Assessments occur at 2 and 4 weeks of *ad libitum* use, the typical time frame that symptom change would be detected from pharmacological treatment (e.g. SSRI). Details regarding marijuana strain assignment procedures, sample ascertainment, timing of assessments, power analyses, and the analytic plan follow.

As an exploratory endpoint, we will track participant's self-reported anxiety level, marijuana use, and sleep pattern with *daily follow-up messages* (online via email and the RedCap tool) over the course of the 4-week study period. This aspect will provide important data on patient choice, patient behavior, and edible impact on anxiety.

After the first two weeks (of four), all participants will return to the CINC (Creativity for Innovation & Creativity) laboratory (**2-Week Appointment, Session 2**) to complete the full set of biological measures and nearly all of the self-report measures and exercises with the elimination of one acute stressor (Rumination Induction) and the addition of one short survey on symptom change (Patient Global Impression of Change). After two more weeks (four weeks after the beginning of the study period), a final set of measures will be collected in our Mobile Van Pharmacology and Phlebotomy Laboratory (**4-Week Mobile Appointment: Pre & Post self-administration, Sessions 3 & 4**), to assess the longer/chronic (4-week, pre-administration, Session 3) and shorter/acute (0-1 hour, post-administration, Session 4) effects of cannabis use on all measures. Two additional measures will be added at this point to report the participant's current feelings after cannabis self-administration (Addiction Research Center Inventory (ARCI) and Drugs Effects Questionnaire (DEQ)).

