While the main portion of the study will be complete after this 4-Week Appointment, we will continue to track participant's self-reported anxiety level, sleep pattern, and marijuana use with a *monthly follow-up survey* (online via email and the RedCap tool), over the course of a five-month follow-up, in keeping with the exploratory nature of the design. This aspect will provide important data on patient choice, patient behavior, and the effects of other marijuana products on anxiety.

In sum, the study will involve a 4 (marijuana-user groups: +THC/-CBD, , +THC/+CBD,, -THC/+CBD, and non-users) x 4 (Session: 1, 2, 3, and 4) mixed factorial design. The complete

schedule of assessments and measures taken at each assessment are outlined in Table 1 and described below.

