Because the long-term goal of this work is to better understand the effect of different levels of cannabinoids in anxiety patients, as they are used real world, we decided that it was critically important to emphasize external validity in both the flower and edible forms of cannabis use. The disadvantage of our design is that we have little control over how the participants use the marijuana or how much they use. To address this limitation, both in our pilot study and in this application, we rely on blood quantitation of cannabinoids (from both flower and edible users) to determine the level of THC and CBD in each subject. Thus, regardless of how the participant uses the marijuana, we have an objective measure of the dose received for both THC and CBD for each subject, which is the sine qua non of pharmacological research. This aspect is also critical for our analytic approach, which allows for the analysis of THC and CBD blood levels as continuous measures. In this way, we also capitalize on the greater variability in blood levels expected in the design by analyzing overall levels of CBD and THC as well as by strain, which by design (in flower and edible forms) will have different THC/CBD ratios. This further allows for a direct test of whether any differences in outcomes for participants randomly assigned to the -THC/+CBD strain are due to an increase in CBD or a decrease in THC as compared to their Baseline. This strain is a critical comparison as there are data to suggest that the effects of THC differ when CBD is also in the blood.

**Power Analysis and Sample Size Requirements.** Sample size was selected to permit analysis of the primary research questions at two-tailed alpha of .05 and power level of .80. Estimates of effect size follow Cohen and were conducted in G\*Power 3. The primary analyses in **Aims 1-3** broadly is the test of the group X time interaction effects across repeated assessments of THC/CBD and anxiety, inflammatory markers, and stress reactivity. For the current data analysis plan, we will only focus on the ratios and time points that we currently have supporting preliminary data for and hypothesize to have the greatest impact on anxiety. Hence, in this data analysis plan we will focus on the 3 main time points (out of 4) for a chronic use endpoint [Baseline, 2 Week, and 4-Week Pre-administration (Sessions 1-3)] and the 3 main cannabis product so that there will be

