an all THC, all CBD, and a combination of THC to CBD group [(+THC/-CBD, +THC/+CBD, and -THC/+CBD, ratios: 1:0, 1:1, and 0:1)].

[figure not shown]
[figure not shown]
To be conservative, we thus estimated an ICC of .50. Using a mixed model ANOVA design, with four groups, three assessment points, and an average ICC = .5 between assessment points, a total  $n=450$  (75 per flower group and the control, and 50 per edible group) will allow us to detect a groupXtime interaction effect as small as  $f=.09$ . In **Aim 2B**, the test of the effects of group on stress-reactivity will again involve four groups ( 3 cannabis and 1 control) but only one assessment point.. Note that our power analysis is conservative, as our actual analysis will involve more powerful tests (e.g., focused interaction contrasts as opposed to overall  $F$  tests). For **Aim 3**, the estimation of the mediational model via path analysis (Hypothesis 3; see Figures 3a and 3b below), Monte Carlo simulation strategies formed the basis of our power analysis. Given that the model in Figure 3b is the more complex of the two, we utilized the model structure with the three planned contrasts as exogenous variables in our simulations. The key test of Hypothesis 3 will involve the use of structural equation modeling techniques. Because we have almost no empirical data on which to base estimates of effect size, we conservatively utilized small to moderate effect sizes depending upon hypothesized relationships. For example, we expect small coefficients (.20) from each contrast to stress reactivity, whereas we expect a slightly larger path (.40) between the contrast comparing the -THC/+CBD strain to control and inflammation. Power analyses were conducted in Mplus and then in SAS following procedures for estimating the power of the likelihood ratio test of the significance of parameters in structural equation models. We utilized Monte Carlo simulation to generate a population covariance matrix based on the hypothesized parameters in the model. For the smallest path in the model (which requires the most power to test), assuming two-tailed alpha of .05, our estimates of power at various sample sizes appear in Table 3. To assure .80 power or better to detect small associations between all groups, we thus require data from 450 participants (75 in the control and each flower group as well as 50 in each edible group) for our mediational analyses.

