**Specific Aim 1** – To compare changes in anxiety in mild to moderately anxious marijuana users exposed to 4 weeks of use of one of three different marijuana strains (+THC/-CBD vs. +THC/+CBD vs. -THC/+CBD) to a group of non-using controls matched on anxiety. *Hypothesis 1* predicts a main effect of strain such that -THC/+CBD marijuana users will have lower levels of anxiety (BAI) compared to other marijuana groups and to non-using controls. To examine the main effects of group on these outcomes, we will estimate a random coefficient regression (RCR) models in SAS Proc Mixed wherein the change in BAI scores will be regressed on marijuana user group, time, and the groupXtime interaction. *Hypothesis 1* also predicts that higher CBD levels in blood among marijuana users will be associated with lower BAI. The analysis for this hypothesis will again be a RCR model, but instead of group membership, the independent variables in these models will be level of CBD in blood, time, and the CBDxtime interaction. We will conduct additional models to explore whether there may also be main effects of THC in blood or a THCXCBD interaction effect on BAI. Secondary models will test the effects of strain and /or cannabinoid blood levels on the daily and monthly assessments of anxiety using a multi-level modeling approach. These additional analyses will appropriately control for Type I error, depending upon the number of tests run. Co-I [name] has used such models extensively in prior work.

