**Specific Aim 2** - To assess inflammation and stress reactivity [biological and behavioral stress change scores during a stress induction (TSST)] in mild to moderately anxious marijuana users exposed to 4 weeks of use of one of three different marijuana strains compared to a group of non-using controls matched on anxiety. *Hypothesis 2A* predicts a main effect of strain such that -THC/+CBD marijuana users will have lower levels of circulating peripheral inflammatory markers compared to other marijuana groups and to non-using controls. To examine the main effects of group on these outcomes, we will estimate a random coefficient regression (RCR) models in SAS Proc Mixed wherein the summary values of the panel of inflammatory markers utilized in our preliminary study will be regressed on marijuana user group, time, and the groupXtime interaction. *Hypothesis 2A* also predicts that higher CBD levels in blood among marijuana users will be associated with lower levels of circulating peripheral inflammatory markers. The analysis for this hypothesis will again be a RCR model, but instead of group membership, the independent variables in these models will be level of CBD in blood, time, and the CBDxtime interaction. We will conduct additional models to explore whether there may also be main effects of THC in blood or a THCXCBD interaction effect on inflammatory markers. *Hypothesis 2B* predicts a main effect of strain on reduced stress reactivity. RCR models in SAS will again be utilized, wherein stress reactivity (pre-rumination induction–post rumination induction change scores of self-report, state anxiety, and inflammatory markers) will be regressed on marijuana user group. *Hypothesis 2B* also predicts that higher CBD levels in blood among marijuana users will be associated with even lower stress reactivity. As in the test of *Hypothesis 2A*, we use RCR wherein the independent variables in these models will be level of CBD in blood. As with Aim 1, we will conduct additional models to explore whether there may also be main effects of THC in blood or a THCXCBD interaction effect on stress reactivity, with appropriate Type 1 error corrections.

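### The strain hypotheses are given only a four-level group term that includes the non-randomised non-users, and no contrast among the randomised arms is defined for Aims 1 and 2

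*Combined protocol and SAP*

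**What the plan says.** For Hypothesis 1, the Statistical Analysis Plan in Section IV "predicts a main effect of strain such that -THC/+CBD marijuana users will have lower levels of anxiety (BAI) compared to other marijuana groups"; the non-users are named as a further comparator. Hypotheses 2A and 2B also predict a main effect of strain. The analysis sentence shared by Aims 1 and 2A reads "To examine the main effects of group on these outcomes, we will estimate a random coefficient regression (RCR) models", and the Aim 1 model is one "wherein the change in BAI scores will be regressed on marijuana user group, time, and the groupXtime interaction". Aim 2A has the same three terms. Aim 2B regresses stress reactivity on the group factor alone, without time.

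The Section IV overview defines the factor. Its levels are the three strains "and non-users) x 4 (Session: 1, 2, 3, and 4) mixed factorial design". The power section uses the same structure: "Using a mixed model ANOVA design, with four groups, three assessment points", and four groups again for Aim 2B.

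Users are randomised to strain (Section XII, Baseline Appointment). Non-users are not assigned (Section I). They are selected for six months without use and no wish to use cannabis for anxiety (Section VI), and the stated matching is a GAD-7 score of at least 5 (Section IV overview).

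The overview also says that the randomised 1:0 strain "serves as a naturalistic control group and our primary hypotheses surround effects of switching anxious marijuana users" to the 1:1 or 0:1 strain.

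The power section adds that the actual analysis will use focused interaction contrasts rather than overall F tests. It defines none for Aims 1 and 2. The one contrast it describes, for Aim 3, sets -THC/+CBD against control.

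**The concern.** A four-level group term pools a randomised comparison (strain v strain) with a non-randomised one (users v non-users). It is non-null whenever users as a whole differ from non-users, even if the three strains act identically. Such a difference could come from selection, expectancy, or buying and using a product at all.

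If the analysis is carried out as written for Aims 1 and 2, a significant group or group x time term could be reported under the name strain when it reflects only user status. The global hypothesis concerns the THC:CBD ratio, and randomisation protects only the comparison among users, so the written test does not by itself answer the main question. The users-only models in the plan do not fill the gap. They use blood CBD and THC, which are not randomised exposures under ad libitum use.

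The baseline check shows the same mixing: it assesses the success of random assignment across the three user groups and the control group together.

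**Working it through.** **Inputs from Section IV, power analysis.** "two-tailed alpha of .05 and power level of .80"; a design "with four groups, three assessment points, and an average ICC = .5 between assessment points"; total N = 450, with 75 per flower strain, 50 per edible strain and 75 controls. Each strain therefore has 75 + 50 = 125, giving 3 × 125 = 375 randomised users and 75 non-users. The stated detectable effect is f = .09 for group x time.

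**Assumed input.** A user v non-user gap d of 0.2, 0.3 or 0.4 SD in Session 1 to 3 change. The documents give no figure.

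**The plan's own figure.** For the within-between interaction, λ = f²·N·m/(1 − ρ), with df (k − 1)(m − 1) and (N − k)(m − 1).
- λ = .09² × 450 × 3/.5 = 21.87 on (6, 892) df, which gives power .96.
- The effect detectable at 80% power is f = .071, so f = .09 is not reproduced as the 80% limit. The discrepancy is conservative and does not affect this point.

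**Omnibus test with identical strains.**
- 3-df group term on change. At ρ = .5 the variance of change is 2(1 − .5)σ² = σ², so the SD of change equals the raw SD. Then λ = d² × 75 × 375/450 = 62.5·d² on (3, 446) df.
- 6-df group x time term, with the gap growing linearly as 0, d/2, d over Sessions 1 to 3. The squared deviations over time sum to d²/2, so λ = 62.5 × (d²/2)/.5 = 62.5·d² on (6, 892) df.

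| d (SD) | λ | P(reject), 3 df | P(reject), 6 df |
|---|---|---|---|
| 0.2 | 2.5 | .23 | .17 |
| 0.3 | 5.625 | .49 | .38 |
| 0.4 | 10.0 | .76 | .64 |

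Simulation (20,000 runs) confirmed the 3-df column. For Aim 2B, which has one assessment point, the 3-df column applies with d in SDs of the reactivity score.

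**Randomised comparison with identical strains.** A three-arm test on users only rejects at .05 whatever d is (simulated .048 to .052). The 0:1 v 1:0 contrast taken from the four-group model also rejects at about .05 for gaps from 0 to 0.5 SD.

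**Rate of falsely supporting the ordering.** In simulation at d = 0.2, 0.3 and 0.4, a significant omnibus term together with 0:1 significantly below 1:0 occurs in about 2% of runs. Requiring 0:1 to be significantly below 1:1 as well brings this to about .004 to .005.

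**Power of the randomised test at f = .09.**
- With f = .09 within the three arms: λ = .09² × 375 × 3/.5 = 18.225 on (4, 744) df, power .94.
- With f = .09 across four groups, equal steps s from 1:0 to 1:1 to 0:1, and controls equal to 1:0: the between-group sum of squares is 312.5·s² for four groups and 250·s² for three arms. Then λ = 21.87 × 250/312.5 = 17.50, power .93.
- In that second scenario the unadjusted 1-df contrast 0:1 v 1:0 has power .99, and the 2-df contrast x time test .97.

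**The case against.** The plan does not say that it will rest on the omnibus F. The power section uses that test to set the sample size and calls the calculation conservative because focused contrasts will follow. Hypothesis 1 is directional and stepwise, so a significant four-group F could not support it without comparisons between arms. Those comparisons are estimable from the four-group model and hold their error rate. Comparing each strain with non-users is itself a stated aim, so controls belong in the analysis.

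Much of this stands, and it rules out three stronger readings that a reader might infer. One is that the design has no uncontaminated test of strain: it has one, which is left unspecified. Another is that .23 to .76 is the false-positive rate for Hypothesis 1. It is the rate for one term, whose null of four-group equality really is false in that scenario. The third is that the models are identical across aims: Aim 2B has no time term.

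What does not stand is that the mention of contrasts settles the matter. It is a single example given in the power section. The Aim 1 and Aim 2 analysis text defines no contrast, and the only one described is against control. Figure 3b was not available for this check. It belongs to Aim 3 and would not supply contrasts for Aims 1 and 2.

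**Conclusion.** The point holds in a limited form. The term written for the strain hypotheses answers a different question from the one asked, and the randomised comparison against 1:0, which the overview places at the centre of the primary hypotheses, has no defined test in Aims 1 and 2. Followed as written, the omnibus term would be significant in roughly a sixth to three quarters of trials with identical strains, over gaps of 0.2 to 0.4 SD.

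Those figures rest on an assumed gap, 450 analysed participants, ρ = .5 and, for the 6-df test, linear divergence. They show how readily the term responds to user status alone. They do not forecast false claims about the predicted ordering. This is more than missing detail, because nothing in the text stops a user v non-user difference from being labelled a strain effect.

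**What to change.** For Aims 1, 2A and 2B, name the comparison among the three randomised arms as the confirmatory strain test: a 2-df strain term, or a 4-df strain x time term for Aims 1 and 2A. Pre-specify the contrasts 0:1 v 1:0 and 1:1 v 1:0. Fit these either in users only or as contrasts within the four-group model. Report each strain v non-users, and all users v non-users, separately and labelled observational. State that conclusions about strain or ratio rest only on the randomised contrasts.

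The cost is SAP wording and a re-specified test, with no new data. Omnibus power at f = .09 goes from .96 to about .93 to .94.

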#### **IV. RESEARCH STUDY DESIGN**

---

**Overview and Design of the Proposed Study.** Consistent with our preliminary study, we will recruit (from the Denver and Boulder areas): 450 participants who report a desire to use marijuana to cope with their anxiety, have had previous experience with marijuana, and report a Generalized Anxiety Disorder-7 (GAD-7) score of  $\geq 5$  (at least mild to moderate anxiety) and 75 non-using cannabis controls (matched for anxiety via GAD-7  $\geq 5$ ) who do not report an intention to use marijuana to cope with their anxiety nor any marijuana use over the prior six months. A summary of the Assessment schedule and the additional inclusion/exclusion criteria are detailed below in Table 1 and Section VI (respectively).

All participants will come to the CUChange Lab for a Baseline Appointment (Session 1) involving extensive measures of anxiety (e.g., Depression, anxiety, and stress scale, a rumination induction task, a dot probe task, rumination self-report scale, etc.) and other psychiatric symptoms, health behavior (e.g., stress, quality of life, sleep, alcohol use), the cognitive testing battery utilized in our preliminary studies, a blood draw for biomarkers of inflammation, and a motor battery (**Baseline Appointment, Session 1**). During this Baseline Appointment, a research assistant will provide information on three at-home aspects of the study: 1) the range of assigned cannabis products (e.g., differing THC to CBD ratios possible) and potential prices, 2) the ActiGraph wearable watch device that participants will be loaned to measure physical activity and sleep (during the final 2 weeks of the four week study), and 3) a microbiome collection kit that they will be given to complete (once before and once after 4 weeks of *ad libitum* use of their cannabis product). The experimental aspect of this study will be the assigned cannabis ratio, while the other aspects of this study are *ad libitum* based, with regard to the dosing schedule and choice of product type (flower or edible), by participants that would already like to use cannabis to cope with their anxiety.

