**Specific Aim 3** - To test indirect effects of marijuana use on anxiety (BAI) via inflammatory markers and stress reactivity in anxious marijuana users exposed to 4 weeks of use of one of three different marijuana strains compared to a group of non-using controls matched on anxiety. Hypothesis 3 will test mediational models that ask whether the effect of marijuana use and strain on anxiety is mediated by changes in inflammation, stress reactivity, or both. To this end, we will estimate the mediational models in Figures 3a and 3b via structural equation modeling. To test the overall effect of use of marijuana versus non use, we will estimate model 3a wherein the sole exogenous variable is marijuana users (coded as 1) versus non-users (coded as 0). The mediators will be change in inflammation from Session 1 to Session 3 and stress reactivity at Session 3. The outcome variable is change in anxiety from Session 1 to Session 3. This model will be estimated and both the fit of the model and the significance of the path coefficients will be examined. Importantly, we will compare the path coefficients from user status to inflammation versus stress reactivity to determine whether use is associated with changes in inflammation, stress reactivity, or both. Assuming that the paths from inflammation and stress reactivity to anxiety are significant, we can test whether there are indirect effects of user status on anxiety that are mediated by inflammation, stress reactivity, or both. A test for completeness of mediation is employed through a 1 degree of freedom  $\chi^2$  test where a path directly from user status to anxiety is added to the model. A nonsignificant direct path and a nonsignificant change in  $\chi^2$  suggest that user group effects on the anxiety were mediated through the theoretical mediational constructs. A secondary test of mediation will utilize bootstrap methods to test the significance of, and confidence limits around, the mediated effect. Similar mediational analyses have been widely used by Co-I [name]. The model depicted in Figure 3b will test the more focused hypothesis that the ratio of cannabinoids is critical for the biological and behavioral changes that drive anxiety. The analysis will follow identical procedures to those described to test Model 3a. Finally, it is also possible to use continuous values of THC and CBD in blood as the exogenous predictors in the model.

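### Aim 2B and the mediation models use Week 4 stress reactivity without the Session 1 value, so an existing difference between users and non-randomised non-users passes into the control contrasts and the user path

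*Combined protocol and SAP*

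**What the plan says.** Strain is randomised among users only (Section IV, Marijuana Administration at Home; Section XII, Baseline Appointment). The control consists of people without recent cannabis use who must not want cannabis for their anxiety, whereas users must want it (Section VI, inclusion criteria 4 to 6). The matching described is that both meet GAD-7 of at least 5 (Section IV, Overview).

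The Statistical Analysis Plan then specifies:

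- **Aim 1:** "the change in BAI scores will be regressed on marijuana user group, time, and the groupXtime interaction". Aim 2A has the same terms. The power section takes Sessions 1 to 3 as the analysed time points.
- **Aim 2B:** "change scores of self-report, state anxiety, and inflammatory markers) will be regressed on marijuana user group". These are changes from before to after the induction within a session. The power section says that this test involves four groups "but only one assessment point".
- **Aim 3:** in Model 3a user status is the only exogenous variable. The mediators are "change in inflammation from Session 1 to Session 3 and stress reactivity at Session 3", and the outcome is Session 1 to 3 change in anxiety. Model 3b follows the same procedures.

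Contrasts with the control are planned. Hypotheses 1, 2A and 2B rank the strains against it, and the mediation power calculation refers to "the contrast comparing the -THC/+CBD strain to control and inflammation".

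Baseline reactivity is collected. The Overview lists among the Session 1 measures "a rumination induction task, a dot probe task, rumination self-report scale, etc"; Table 1 drops the induction only at Week 2; and Section XII counts the Week 4 inductions as the second and third. The only adjustment mentioned is in Table 2, which allows BAI and BDI-II differences to be covaried if that proves necessary, without a criterion.

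**The concern.** Users and controls differ by selection in how they deal with anxiety, so they may well differ in reactivity to a rumination task before any study product is bought. The within-session difference in Aim 2B does not remove such a gap, because reactivity is itself that difference. Only the Session 1 measurement carries the information, and neither Aim 2B nor Models 3a and 3b use it.

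Model 3a adds a second difficulty. The plan compares the path from user status to inflammation with the path to reactivity, to decide which of them changes with use. One path is corrected for baseline and the other is not. A pre-existing gap could therefore make reactivity look like the mechanism. If reactivity also predicts anxiety change, the false user path carries into the indirect effect.

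**Working it through.** **The plan's own figure.** For the group by time test the plan states f = .09 with N = 450, four groups, three assessments, ICC .5 and power .80. With lambda = f² × N × m / (1 − rho) = .0081 × 450 × 3 / .5 = 21.87 on 6 and 892 df, power at f = .09 is .958; the smallest f at power .80 is .071. The figure is not reproduced, but the difference is on the safe side and does not affect this point. For Aim 2B the text gives no detectable effect. A one-way F test with N = 450 and four groups gives f = .156.

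**Inputs.** 75 per flower strain, 50 per edible strain and 75 controls (power section) give 125 per strain, 375 users and 75 controls. Two-sided alpha is .05. The size of the gap d (0.1 to 0.3 SD) and the Session 1 to 3 correlation of reactivity r (.3 or .5) are assumptions; the plan's ICC of .50 is for the group by time assessments.

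**Step 1: Session 3 alone.** A stable gap d is the bias. SE = sqrt(1/n1 + 1/n2), and the rejection rate is P(|Z + d/SE| > 1.96).

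| Contrast | SE | d = 0.1 | d = 0.2 | d = 0.3 |
|---|---|---|---|---|
| One strain v control (125 v 75) | 0.146 | 10.5% | 27.8% | 53.7% |
| Users v non-users (375 v 75) | 0.126 | 12.4% | 35.3% | 66.0% |

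The second row is the error rate on the path from user status to reactivity, not on the whole indirect effect.

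**Step 2: using Session 1, users v non-users, d = 0.3.** With baseline as covariate, bias = d(1 − r) and SE is multiplied by sqrt(1 − r²). With change, the stable gap cancels.

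- r = .5: bias 0.15, SE 0.1095, rejection about 28%.
- r = .3: bias 0.21, SE 0.1207, rejection about 41%.
- Change: bias 0, rejection 5%.

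**Step 3: the opposite assumption.** If the same 0.3 SD gap regresses to a common mean (r = .5), the bias is 0.15 with Session 3 alone, 0 with the covariate, and 0.15 with the opposite sign for change. Under both assumptions the covariate model is less biased than Session 3 alone. Neither the covariate nor change is right under both.

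**Step 4: randomised strain contrasts.** The expected baseline gap is zero, so there is no bias. The detectable difference in Aim 2B is 2.80 × sqrt(2/125) = 0.35 SD. With the covariate at r = .5 it is 2.80 × sqrt(0.75 × 2/125) = 0.31 SD.

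**Step 5: Aims 1 and 2A.** Session 1 is an analysed time point or is subtracted, so a stable gap drops out. Only differential change between users and controls would bias those control contrasts.

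**The case against.** The strongest reply is that the plan's main question does not depend on the non-using control. Section IV calls the THC-only strain a naturalistic control and places the primary hypotheses on switching users to the other two ratios. That comparison is randomised. This stands: a reader might infer that the ratio conclusions are confounded, or that the plan leaves open where they rest, and the documents support neither. The problem is confined to contrasts with non-users and to the mediation models that include them.

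A reader might also infer that the plan ignores baseline throughout. It does not: Session 1 enters Aims 1 and 2A, although the wording does not settle whether as a response or by subtraction. Leaving sex and product form out of the strain models costs precision but does not bias the strain contrasts, since group sizes are equal across strains within each form.

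Two further objections stand in part. The error rates rest on assumed gaps, so they show sensitivity and do not predict an error. And Aim 2B includes inflammatory reactivity, whereas Section XII lists one blood draw per session; a Session 1 value for that component therefore does not appear to be available. It is clearly available for the analogue ratings around the induction.

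**Conclusion.** The point holds for Aim 2B control contrasts and for the stress mediator in Models 3a and 3b. A stable, pre-existing reactivity gap of 0.1, 0.2 or 0.3 SD would give false-positive rates of about 10%, 28% and 54% for one strain against control, and 12%, 35% and 66% on the user path, against a nominal 5%. These rates assume unit variance, completers at the planned sizes and a gap that does not change over four weeks.

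For Aims 1 and 2A the concern is narrower: differential change between users and controls is not addressed by any covariate set fixed in advance, and the provision in Table 2 has no rule. The randomised strain evidence is sound. The change is worth making because it uses data already collected, reduces the bias under either assumption examined, and improves precision for the strain contrasts.

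**What to change.** 1. In Aim 2B, and for the stress mediator in Models 3a and 3b, enter Session 1 self-report reactivity (the analogue ratings around the induction) as a covariate. Show Session 1 to 3 change in reactivity as a sensitivity analysis, because the two rest on different assumptions. Do not promise this for inflammatory reactivity. Confirm the rating range first: the 4-Week Appointment text gives 1 to 100 and Table 2 gives 0 to 10, which matters for the change analysis.
2. Report strain v control contrasts and Model 3a as observational, with a fixed set of covariates already collected, such as age, sex, GAD-7, BDI-II and AUDIT, in place of the conditional wording in Table 2. Base the ratio conclusions on strain contrasts among randomised users, in line with Section IV, with sex and product form as covariates. Product form applies to users only.
3. Leave the control out of the test of random assignment in the Statistical Analysis Plan; it was not randomised.

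The cost is SAP wording and a few degrees of freedom. The gain in Aim 2B is a detectable strain difference of 0.31 instead of 0.35 SD at r = .5. The limit should be stated: with a stable 0.3 SD gap the covariate model still rejects about 28% of the time on the user path (41% at r = .3), against 66% unadjusted, and fixed covariates remove only the selection that they measure.
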